Can edoxaban and rivaroxaban be prescribed for breastfeeding mothers?

The New Horizons Study

Protocol Short Title/ Acronym: The New Horizons Study

Version 1.4 30/10/2023

Trial Identifiers

IRAS Number:	1005067
Other Trial Identifiers:	Sponsors Identifier: 3631

Sponsor

Name of organisation(s):	King's College Hospital
Sponsor contact:	[name]
Address:	King's Health Partners Clinical Trials Office, [name]
[contact]
Fax:	n/a
Email:	[contact]

Chief Investigator

Name:	[name]
Address:	Department of Haematological Medicine, KCH
[contact]
Email:	[contact]

Research Team:

Name:	[name]
Address:	Department of Haematological Medicine, King's College Hospital / Institute of Pharmaceutical Science, King's College London
[contact]
Email:	[contact]

Name:	[name]
Address:	Analytical Services International Ltd, [name]
[contact]
Email:	[contact]

Name:	[name]
Address:	Analytical Services International Ltd, [name]
[contact]
Email:	[contact]

Trial Protocol Version History Summary

Protocol Version Number	Issue Date	Summary of Significant Changes
1.2	26/07/2022	Initial submission
1.3	19/09/2022	Changes following feedback from REC and MHRA
1.4	30/10/2023	Extension of eligibility criteria for recruitment and reflection of this change in primary and secondary endpoints

1. Study Synopsis

Title of clinical trial	Can edoxaban and rivaroxaban be prescribed for breastfeeding mothers?
Protocol Short Title/Acronym	The New Horizon's Study
Trial Phase if not mentioned in title	IV
Sponsor name	King's College London
Chief Investigator	[name]
IRAS number	1005067
Purpose of clinical trial	To determine whether it would be safe for breastfeeding mothers to be prescribed edoxaban or rivaroxaban during the postnatal period
Primary objective	To determine if edoxaban and rivaroxaban are excreted into breastmilk to clinically relevant concentrations when volunteer breastfeeding women take the IMP for 3 consecutive days within the 12 week postpartum period.
Secondary objective (s)	
To describe the concentration-time profiles of edoxaban and rivaroxaban in the plasma and breastmilk of breastfeeding mothers within the 12 week postpartum period, following daily dosing for 3 consecutive days and therefore to establish the potential exposure of breastfed infants to edoxaban and rivaroxaban.
 
To determine the extent of edoxaban transfer into human breastmilk within the 12 week postpartum period.
 
To determine the extent of rivaroxaban transfer into human breastmilk within the 12 week postpartum period.

Trial design	Open-label, single-centre study of breastfeeding mothers within the 12 weeks post-partum period.
Endpoints	N/A
Sample size	12 (6 in the edoxaban arm, 6 in the rivaroxaban arm)
Summary of eligibility criteria	Women ≥ 18 years of age, within the 12 week postnatal period, who agree to stop breastfeeding their infant during the plasma and breastmilk sampling phase
IMP, dosage and route of administration	Edoxaban 60mg oral film coated tablets Rivaroxaban 20mg oral film coated tablets
Maximum duration of treatment of a participant	3 days
Version and date of protocol amendments	1.4 30 th October 2023

2. Glossary of Terms

AE	Adverse Event
AR	Adverse Reaction
CA	Competent Authority
CI	Chief Investigator
CRF	Case Report Form
CRO	Contract Research Organisation
CTA	Clinical Trial Authorisation
CTIMP	Clinical Trial of Investigational Medicinal Product
CTU	Clinical Trials Unit
DMC	Data Monitoring Committee
DSUR	Development Safety Update Report
EC	European Commission
EMA	European Medicines Agency
EU	European Union
EUCTD	European Clinical Trials Directive
EudraCT	European Clinical Trials Database
GCP	Good Clinical Practice
GMP	Good Manufacturing Practice
IB	Investigator Brochure
ICF	Informed Consent Form
IMP	Investigational Medicinal Product
IMPD	Investigational Medicinal Product Dossier
ISF	Investigator Site File (This forms part of the TMF)
ISRCTN	International Standard Randomised Controlled Trials Number
MA	Marketing Authorisation
MHRA	Medicines and Healthcare products Regulatory Agency
NIMP	Non-Investigational Medicinal Product
PI	Principal Investigator
PIC	Participant Identification Centre
PIS	Participant Information Sheet
QA	Quality Assurance
QC	Quality Control
QP	Qualified Person
RCT	Randomised Control Trial
REC	Research Ethics Committee
SAE	Serious Adverse Event
SAR	Serious Adverse Reaction
SDV	Source Data Verification
SOP	Standard Operating Procedure
SmPC	Summary of Product Characteristics

It is well established that there is an elevated risk of VTE during pregnancy, which continues during post-partum period (Treffers, *et al.* 1983; Ray and Chan, 1999; Simpson, *et al.* 2001; Soomro, *et al.* 2002; Heit, *et al.* 2005; James, *et al.* 2009). The risk of post-partum VTE is as much as 5 times higher than during pregnancy and 2.5 to 84 times greater than in non-pregnant women (Heit, *et al.* 2005; Salonen Ros, *et al.* 2001; Sultan, *et al.* 2012; Tepper, *et al.* 2014), and PE has been and remains a leading direct cause of maternal death in the UK for over 20 years (Centre for Maternal and Child Enquiries, 2011). The duration of the increased VTE risk after childbirth varies based on the type of risk factors and the risk can extend up to the first 3 to 6 weeks post-partum (Sultan, *et al.* 2014).

LMWH is commonly prescribed as thromboprophylaxis during both pregnancy and the post-partum period because it does not cross placenta and is reported to be safe during breastfeeding. Although warfarin use in pregnancy is restricted, it is reported to be safe to use during breastfeeding (Bates, *et al.* 2012).

In the UK, the timing of initiation and duration of post-partum thromboprophylaxis depends on the type of and the number of existing risk factors of postnatal VTE. Anticoagulation treatment for the management of VTE should be initiated immediately once DVT or PE is clinically suspected, until the diagnosis is excluded by objective testing. The maintenance of therapeutic doses of subcutaneous LMWH should be continued until at least 6 weeks postnatally, and the continuing risk of thrombosis should be assessed before discontinuing treatment. In place of LMWH, warfarin can be prescribed following birth in breastfeeding women.

Although direct oral anticoagulants (DOACs) offer many advantages, they have not been tested in breastfeeding women, thus have not been recommended in breastfeeding women who need treatment for post-partum VTE (Royal College of Obstetricians and Gynaecologists, 2015b).

Direct oral anticoagulants

DOACs, including direct anti-Xa inhibitors (rivaroxaban, apixaban and edoxaban) and the thrombin inhibitors (dabigatran), directly inhibit coagulation proteins in the coagulation cascade. Apixaban, rivaroxaban and edoxaban selectively and reversibly bind to factor Xa, competitively inhibiting both free and clot-bound factor Xa and prothrombinase activity, inhibiting thrombin formation. Dabigatran blocks the procoagulant activity by competitively and reversibly binding to the active site of free and fibrin-bound thrombin, preventing the conversion of fibrinogen into fibrin during the coagulation cascade. These four DOACs are currently available in the UK, for the treatment and prevention of VTE.

A number of clinical trials and post-marketing studies have demonstrated that fixed doses of edoxaban and rivaroxaban have improved or similar efficacy and non-inferior safety compared to warfarin or LMWH for prevention and treatment of arterial and venous thrombotic diseases, because of their predictable pharmacokinetic profile (Agnelli, *et al.* 2013; Hokusai-VTE Investigators, *et al.* 2013). The most severe side effect of edoxaban and rivaroxaban is major bleeding.

Previous non-clinical and clinical studies/case reports on DOACs in breastmilk

Previous preclinical animal studies indicate that DOACs are secreted into rat milk. The excretion of dabigatran into milk varies from 0.08 to 0.13% of the dose administered to the lactating rats (European Medicines Agency, 2008). A single oral dose of apixaban administered to lactating rats was extensively secreted into rat milk with a high milk to maternal plasma ratio (C_{max} M/P about 8, AUC M/P about 30) (Wang, *et al.* 2011). Similarly, rivaroxaban and edoxaban were excreted into the milk of rats although the maternal plasma ratio has not been published (Xarelto 10 mg - Summary of Product Characteristics (SPC) - (EMC), 2015; Lixiana - Summary of Product Characteristics (SPC) - (EMC), 2015).

There are a few published clinical case reports describing the use of DOACs in postpartum women. A recent case reported that a patient was prescribed rivaroxaban 15 mg twice daily on the fifth day after delivery and demonstrated that a small amount of rivaroxaban passes into human breastmilk (M/P about 0.4), while the safety of rivaroxaban in nursing mothers and their breastfed infants remains to be verified (Wiesen, *et al.* 2016). A recently completed small clinical study indicated that small amount of dabigatran was excreted in breast milk, although the C_{max} M/P and AUC M/P varied significantly between the two breastfeeding women involved in this study (0.04 vs. 0.12 for C_{max} M/P; 0.02 vs. 0.1 for AUC M/P) (EU Clinical Trials Register, 2017).

The work completed by our group (Zhao *et al.* 2020) was the first clinical trial formally investigating apixaban and rivaroxaban's distribution into human breastmilk. Results obtained from three breastfeeding women who were > 6 months post delivery suggested that a small amount of rivaroxaban (milk to plasma ratio (M/P) = 0.26, estimated relative infant dose (RID) = 1.63%) transfers into breastmilk, in contrast to apixaban, which accumulates in milk to significant concentrations (M/P = 2.61, RID = 12.78%).

4. Trial Objectives and Design

4.1. Trial Objectives

Primary objective

To determine if edoxaban and rivaroxaban are excreted in breastmilk to clinical relevant concentrations when volunteer breastfeeding women are administered IMP for 3 consecutive days within the 12 week postpartum period.

Secondary objectives

To describe the concentration-time profiles of edoxaban and rivaroxaban in the plasma and breastmilk of breastfeeding mothers within the 12-week postpartum period, following daily dosing for 3 consecutive days and therefore to establish the potential exposure of breastfed infants to edoxaban or rivaroxaban.

To estimate the milk:plasma ratio of edoxaban and rivaroxaban when taken within 12 weeks postpartum.

4.2. Primary endpoints

Edoxaban concentrations in plasma and breastmilk will be measured 3, 12, 24 hours after swallowing the first 60mg dose of edoxaban and then a second 60mg dose will be taken by volunteers on day 2. On day three, prior to the third 60mg dose being taken, edoxaban samples will be drawn, and repeated at 3, 12, 24 and 72 hrs post third dose.

Rivaroxaban concentrations in plasma and breastmilk will be measured 3, 12, 24 hours after swallowing the first 20mg dose of rivaroxaban and then a second 20mg dose will be taken by volunteers on day 2. On day three, prior to the third 20mg dose being taken, rivaroxaban samples will be drawn, and repeated at 3, 12, 24, 72 hrs post third dose.

4.3. Secondary endpoints

The following PK parameters for edoxaban and rivaroxaban in milk and plasma will be the endpoints: Area under the concentration-time curve (AUC) from zero to 24 hours ($AUC_{(0-24h)}$) on day 1 and day 3 for both breastmilk and maternal plasma.

4.4. Trial design

This is an open-label, single-center study designed to determine the excretion of three consecutive oral doses of edoxaban (EDX group) and three consecutive oral doses of rivaroxaban (RVX group) in the breastmilk of breastfeeding mothers within the 12 weeks post-partum period. The subject population for this study will comprise 12 healthy breastfeeding mothers (6 subjects in each group) who agree to stop breastfeeding their infants during the trial sampling period.

The allocation to the study drugs will be that volunteers will be allocated to the IMP on an alternate basis, e.g. first volunteer allocated to the rivaroxaban arm, second volunteer allocated to the edoxaban arm, with this sequence of allocation then repeated as the trial progresses. Both edoxaban and rivaroxaban are once daily medications. The assessment of concentration and PK profile of edoxaban and rivaroxaban in breastmilk will be conducted through home visits, as outlined in table 4-1 and figure 4-1.

As no human data on edoxaban transfer into breastmilk exists, the edoxaban arm of the trial, will have a 'go – no go' component. After two volunteers have completed the edoxaban arm, interim analysis will be conducted. If significant transfer of edoxaban into breastmilk is found, then the edoxaban arm will cease. However, if not, then recruitment will continue to trial pre-specified target.

4.5. Trial Flowchart

[figure not shown]
Table 4-1: Trial procedures during the clinical trial – EDX and RVX groups

	Pre-sampling		Sampling								Post-sampling		
	Screening	Randomisation	Visit 1 (day 1)				Visit 2 (day 2)	Visit 3 (day 3)				Final Visit (day 6)	
			0 hr	3 hr	12 hr	24 hr	0 hr	0 hr	3 hr	12 hr	24 hr		
Written informed consent	X												
Patient demographics	X												
Eligibility assessment, including vital signs	X	X											
Past medication, medical and social history	X												
Bloods (UEs, LFTs, FBC, coag screen) – safety bloods	X												X
Pregnancy test	X												
Randomisation (if applicable)		X											
Bloods reviewed and volunteer given all clear to take part. Date arranged with volunteer to do the study sampling		X											
IMP dispense		X											
Vital signs and then IMP administration			X				X	X					
Milk sampling (+/- 30min)				X	X	X		X (pre-dose)	X	X	X	X	X

Pharmacokinetic blood samples				X	X	X		X (pre-dose)	X	X	X	X
Adverse events			X	X	X	X		X	X	X	X	X
End of trial for patient												X

Figure 4-1. Milk and blood collection time points – EDX and RVX groups

[figure not shown]
DAY 1

DAY 2

Second dose of EDX / RVX administered.

DAY 3

DAY 6

72 hours post day 3 dose.

5. Trial Medication

5.1. Investigational Medicinal Product

In this trial, subjects will be randomised to either edoxaban or rivaroxaban details of which are described in tables 5-1 and 5-2 below. The trial will use commercially available IMP which will be sourced by Clinical Trials Pharmacy at King’s College Hospital. The IMP will be labelled in line with applicable national and local regulations and will be annex 13 compliant.

Table 5-1 Details of edoxaban

Brand name	Lixiana®
Product name	Edoxaban
Manufacturer	Daiichi Sankyo
Dosage Form	Film-coated tablet
Dose Mass	60 mg
Active ingredient	Edoxaban
Mode of administration	Oral

Table 5-2 Details of rivaroxaban

Brand name	Xarelto®
Product name	Rivaroxaban
Manufacturer	Bayer plc
Dosage Form	Film-coated tablet
Dose Mass	20 mg
Active ingredient	Rivaroxaban
Mode of administration	Oral

5.2. Dosing Regimen

The study drug will be orally administered as tablet (edoxaban or rivaroxaban) formulation once a day on days 1, 2 and 3. The IMP will be administered at subject’s home under the guidance of the investigator with the date and time of administration recorded in the subject’s CRF.

Table 5-3 Dosing regimen

Study Arm	Study Drug Dose	Subjects	Duration for each subject* (Day -28 to day 6)		
Edoxaban (EDX)	60 mg (once daily)	6	Screening (day -28 to -3)	Treatment (day 1 to 3 inclusive)	Safety review (day 6) & study closure
Rivaroxaban (RVX)	20 mg (once daily)	6		Treatment (day 1 to 3 inclusive)	

5.3. IMP Risks

As edoxaban and rivaroxaban have been marketed for many years and are widely prescribed, all effects can be reliably predicted in accordance with their Summary of Product Characteristics (SmPC). It is anticipated that the three single doses of edoxaban or rivaroxaban administered should not create emergencies. But in case there is, a member of the research team will be on call 24 hours a day (through mobile number).

Bleeding as a main risk due to healing of a raw area in the uterus (placental site), which could lead to postpartum haemorrhage with serious consequences, will be highlighted to women, before they consent into the trial.

As it has not been demonstrated if edoxaban or rivaroxaban are safe to prescribe during breastfeeding, study volunteers must stop breastfeeding their infants from the first dose until the follow-up period when the study drugs are undetectable in the maternal plasma.

Full details of AEs of edoxaban and rivaroxaban are listed in the respective SmPCs.

The Reference Safety Information (RSI) for all information pertaining to IMP risk for edoxaban and rivaroxaban are set out in the edoxaban and rivaroxaban SmPC.

Based on both the mechanisms described previously, and on clinical experience with edoxaban and rivaroxaban, the known and potential risks to human subjects can be summarised as follows:

It is recognized that the most common and severe side effect of edoxaban and rivaroxaban is bleeding, especially gastrointestinal bleeding, which may be potentially life threatening and require immediate medical attention. To minimize the risk to subjects, individuals with hepatic disease or history of liver problem associated with coagulopathy and clinically relevant bleeding risk, severe kidney disease or dialysis treatment, lesion or condition if considered a significant risk factor for major bleeding (e.g. gastrointestinal ulceration, presence of malignant neoplasms at high risk of bleeding, very high blood pressure or diabetes without medical control, recent brain or spinal injury, recent brain, spinal or ophthalmic surgery, recent intracranial haemorrhage, known or suspected oesophageal varices, arteriovenous malformations, vascular aneurysms or major intraspinal or intracerebral vascular abnormalities) will be excluded from the study.

There have been uncommon or rare reports of hepatobiliary disorders (e.g. hepatic function abnormal and jaundice), and cardiac disorders (e.g. tachycardia) in patients taking edoxaban or rivaroxaban. Potential subjects will be tested for impaired liver functions as part of screening for eligibility.

Uncommon instances of allergic reactions such as pruritus and allergic oedema have been reported in patients treated with edoxaban or rivaroxaban. Individuals with a history of allergies to DOACs or/and with any history or current clinically significant hypersensitivity or allergic reactions (including known or suspected reactions to any components of the test products) will be excluded from the study. Subjects will also be monitored during the study for systemic hypersensitivity reactions.

The sponsor will immediately notify the chief investigator if any additional safety or toxicology information becomes available during the study. Subjects participating in this study will only be exposed to the IMP for up to 6 days, so the risks outlined in real terms, are extremely small.

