6.1. Inclusion Criteria

To be eligible to participate in this study all the following criteria must be met:

1. Subject is informed and given ample time and opportunity to think about her participation and has provided written informed consent for participation in the study before any study specific procedures take place.
2. Subject is considered reliable and capable of adhering to applicable protocol requirements, including the study drug being administered orally and visit schedule according to the judgement of the Investigator.

3. Women are aged ≥ 18 years.
4. Within the 12 weeks postpartum period.
5. Decision has been confirmed by the volunteer to hold breastfeeding their infant during the study period.
6. Negative pregnancy test.
7. Good physical and mental health, in the opinion of the investigator, determined on the basis of medical history and general clinical examination at screening.
8. Women have clinical laboratory test results within the reference ranges of the testing laboratory: normal renal and liver function, as judged by the chief investigator.
9. Women are not taking any medication interacting with edoxaban or rivaroxaban, as listed in table 5-4 and 5-5.
10. Women are available and permit the research team to make home visits to collect blood and milk samples.
11. Women agree to the study restrictions, as outlined in section 6.3.

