6.3. Study Restrictions

Subjects must be willing and able to adhere to the following prohibitions and restrictions during the course of the study:

Refrain from intake of grapefruit juice from 48 hours prior to dosing and until 24 hours post last dose of IMP;

Refrain from taking drugs of abuse during the study;

Refrain from taking medications during the study as outlined in Section 5.7;

Refrain from breastfeeding their infant during the study.

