6.8. Expected Duration of Trial

The beginning of the trial will be defined as first patient first visit and the end of trial will be defined as database lock.

Active participation in the trial for each volunteer is for 6 days and each individual participant will remain on trial until the morning of day 6 - final visit.

7. Trial Procedures

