7.2. Laboratory Tests

According to the milk and blood collection time points and safety assessment schedule, the blood and milk volumes to be collected from any single subject are presented in Table 7-1.

Blood samples will be packed and transferred to King's College Hospital immediately after collection. Clinical samples (UEs/LFTs/FBC) will be handled by the Viapath, King's College Hospital. Pharmacokinetic blood samples will be cooled and centrifuged as soon as possible in the CI's laboratory at King's College Hospital. The separated plasma samples will be transferred to a clean tube and stored at -20°C.

Milk samples will be stored at -20°C in the CI's laboratory at King's College Hospital. Separated plasma samples and milk samples will then be transferred to ASI Bioanalytics (London, UK) within 56 days for the analysis. Detailed sample collection, handling, labelling, storage and shipment will be described in the Laboratory Manual at King's College Hospital and ASI Bioanalytics.

Table 7-1 Blood and Milk Volumes to be Collected in a single subject in EDX/RVX group over the course of the volunteers involvement in the trial

Assessment	Sample Volume (mL)	No. of Samples	Total Volume (mL)
Safety			
Clinical Chemistry	5.0	2	10.0
Haematology (PT, APTT)	3.7	2	7.4
FBC	2.0	2	4.0
Pregnancy test	3.5	1	3.5
Pharmacokinetic			
Plasma Samples	2.0	8	16.0
Milk Samples	10.0	8	80.0
Total (mL)			Blood: 41.0 Milk: 80.0

FSH: Serum Follicle-stimulating Hormone

Sample volumes are based on direct venepuncture.

Milk sample to be collected at any breast (10ml) by manual expression or breast pump.

Additional samples may be collected as required at the Investigator's discretion. However, the total volume of blood collected per subject during the study will not exceed 100 ml. Individual venepunctures for each time point will be performed. The exact date/time of the milk and blood sample collection will be recorded in the subject's CRF.

Time windows for the collection of the PK blood and milk samples are as follows:
±30 minutes for all sampling time points (with the exception of the pre-dose sample).

8. Assessment of Safety

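### The protocol gives three different end points for the breastfeeding stop, and the one tied to plasma concentration, if measured, cannot be verified when the woman is released on Day 6

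*Protocol*

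**What the plan says.** The protocol describes the end of the breastfeeding stop in three ways.

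- **Drug level.** Section 5.3 (IMP Risks) says the stop runs "from the first dose until the follow-up period when the study drugs are undetectable in the maternal plasma". It gives as the reason that neither drug has been shown to be safe during breastfeeding.
- **Study participation.** Section 6.3 (Study Restrictions) reads "Refrain from breastfeeding their infant during the study". Inclusion criterion 5 in section 6.1 reads "Decision has been confirmed by the volunteer to hold breastfeeding their infant during the study period". Section 6.8 says that "each individual participant will remain on trial until the morning of day 6", and section 7.1.6 and Table 5-3 also close participation on Day 6.
- **Sampling.** The synopsis describes women "who agree to stop breastfeeding their infant during the plasma and breastmilk sampling phase", and section 4.4 describes mothers "who agree to stop breastfeeding their infants during the trial sampling period".

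On sample logistics, section 7.1.6 places the last milk and blood draw, 72 h after the third dose, at the Day 6 visit. Section 7.2 has plasma and milk stored at -20°C and then "transferred to ASI Bioanalytics (London, UK) within 56 days for the analysis".

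**The concern.** The protocol states this stop as a safeguard for the infants, and section 4.4 says that no human data exist on edoxaban transfer into milk. A mother or team member who looks up when breastfeeding may restart gets a different answer depending on the page. The answer in section 5.3 has a second problem. If it means a measured result, nothing in the schedule makes that result available when participation ends. The protocol sets no time for reporting a result, no route for telling the mother, and no scheduled contact after Day 6 for a woman who completes. The follow-up period named in section 5.3 is not defined.

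Early withdrawal widens the gap. Section 6.7 lets a woman leave at any time. If she leaves after the second dose, a restriction that lasts only for the study can be read as lapsing at once, while section 5.3 still applies. The Day 6 sample that might satisfy section 5.3 may then never be taken.

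**Working it through.** There is no stated figure to reproduce. The check is a comparison of passages and date arithmetic.

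**Inputs**
- Third dose: Day 3 (section 5.2).
- Draws after the third dose: 3, 12, 24 and 72 h (section 4.2).
- End of participation: morning of Day 6 (sections 6.8 and 7.1.6).
- Maximum time to transfer: 56 days (section 7.2). The start of that clock is not stated; I assume the day of collection.

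**Step 1: when each wording ends the stop**

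| Wording | Where | Earliest end it supports |
|---|---|---|
| Sampling period | Synopsis, 4.4 | Day 4 or Day 6, depending on how Table 4-1 is read |
| Study | 6.1(5), 6.3 with 6.8 | Morning of Day 6 |
| Not detectable in plasma | 5.3 | No date; depends on a result, or on a presumption that is not stated |

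The first row is ambiguous because Table 4-1 puts the Day 6 visit under its post-sampling heading, yet a milk and blood sample is taken at that visit. The last draw before it is at 24 h: Day 3 + 24 h = Day 4. The Day 6 draw is Day 3 + 72 h = Day 6. The two readings of the sampling period therefore differ by 72 − 24 = 48 h.

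**Step 2: can the section 5.3 condition be known on Day 6, if it is measured?**
- 72 h sample: drawn on Day 6. Latest transfer is Day 6 + 56 = Day 62, before any assay time.
- 24 h sample after the third dose: drawn on Day 4. Latest transfer is Day 4 + 56 = Day 60, also before assay time.

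At release on Day 6 the 72 h sample has only just been taken, and the result of the preceding sample need not exist either. In section 6.7, the text on withdrawal mentions a follow-up visit 1 day (± 1 day) after completion, that is, between Day 6 and Day 8. Table 4-1 does not show that visit, no concentration measurement is assigned to it, and it still comes well before Day 62.

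**The case against.** The strongest reply is that section 5.3 need not require a test. It can be read as describing the follow-up period as the time when drug is expected to have gone. Two places fit that reading: section 5.3 itself puts exposure to study drug at no more than 6 days although dosing takes three, and Table 5-3 places the safety review on Day 6. On that reading sections 5.3, 6.1(5), 6.3 and 6.8 all point to Day 6, and the 56-day limit has no bearing on restart.

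That reading is possible, and it narrows the conflict. But the protocol does not state it and gives no clearance figure to support it. It also leaves the sampling-period wording and early withdrawal unresolved.

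Two further replies carry some weight. The 56 days are a maximum, so earlier analysis is permitted; nothing requires it. Practical instructions may stand in the participant information leaflet or the Laboratory Manual, which are not at hand. They might add detail, but they would not remove the differing statements in the protocol that they are meant to follow. It could also be said that the study runs to database lock, which section 6.8 gives as the end of the trial; the text on the individual participant, however, ends on Day 6.

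**Conclusion.** The point holds. There are three end points for one infant-safety restriction, and section 5.3 is silent on whether its condition is measured or presumed. If measured, it cannot be verified at release, because transfer alone may run to Day 62 against release on Day 6. The Day 62 figure assumes that the clock in section 7.2 starts at collection. The inconsistency between the wordings does not depend on that assumption.

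Some stronger inferences are not supported:

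- **That infants would be exposed to drug on Day 6.** The protocol gives no elimination half-life for either drug in plasma or milk, so residual drug at 72 h cannot be derived from it.
- **That plasma is the wrong fluid to test.** A reader might infer this from the apixaban ratios in section 3 (milk-to-plasma about 30 on AUC, about 8 on Cmax). Those come from rats given a drug not studied here. The human dabigatran ratios in the same section run the other way: 0.02 and 0.1 on AUC against 0.04 and 0.12 on Cmax. The choice of fluid is in any case a clinical decision.
- **That sites would diverge.** The study is single-centre. The risk is that different staff or mothers rely on different passages.

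**What to change.** Reconcile the synopsis and sections 4.4, 5.3, 6.1(5), 6.3, 6.8 and 7.2 into one restart condition, decided by the clinical team and the ethics committee, and use the same wording in each place. The condition should:

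- say whether it rests on a measured result or on elapsed time;
- define its end by a named event rather than by the study or the sampling period;
- cover women who withdraw after one or more doses (section 6.7).

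If a measured concentration is kept, name the sample and what counts as undetectable, and change section 7.2 so that the result is due, and passed to the mother, before the restriction is lifted. Which condition to adopt is not for this review to say.

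The cost is a wording amendment, with the participant information leaflet brought into line. If a measured condition is kept, the relevant sample must also be shipped and assayed earlier for at most 12 women. No change to the sample size or the pharmacokinetic analysis follows.
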